Subjects not eligible for thrombectomy (criterion 3.I) receive less iodine contrast agent and radiation exposure compared to patients undergoing thrombectomy, where iodine is used to navigate during the procedure under X-ray image guidance. Investigational DE-CBCT of these subjects on day 1 imposes varying extent of residual iodine intracranially (from previous standard of care imaging). However, these subjects typically show very relevant imaging features, as hyperacute ischemic changes are challenging yet crucial to visualize. Moreover, DE-CBCT imaging potentially enables iodine removal/suppression. If still hospitalized day 2, an additional DE-CBCT enables diagnostic information about stroke progression.

Subjects that have undergone thrombectomy (inclusion criteria 3.II) will be included one day after admission (day 2), when most of the iodine typically has been filtered out by the kidneys. An absolute GFR (aGFR) and non-renal risk factors for CI-AKI will be assessed before administering iodine contrast agent. These measures will ensure that the risks associated with iodine contrast agents will be minimized.

Similar to above, subjects with a verified intracranial hemorrhage (inclusion criteria 3.III) will be imaged without and with iodine contrast agent day one after assessment of aGFR and non-renal risk factors.

If the subject is deemed inappropriate to receive iodine contrast agent, only imaging without iodine contrast agent will be done. In addition to above, other individual or healthcare aspects may select subjects to undergo only imaging without injection of iodine contrast agent.

6. Study Design

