6.6.2. Procedure for the replacement of subjects

Subjects in the study will be replaced in case of withdrawal of consent or if subject is found ineligible for the study after signing of the informed consent and before the measurement. Subject will also be replaced if patient movement during image acquisition significantly affect assessment of the image material, as judged by the investigator. If only the second scan for subjects included according to 3.I is invalid, they will not be replaced.

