8.2. Sample size justification

Statistical analyses will be performed by Karolinska University Hospital. This is a prospective, open label single centre study. A diagnostic study using DE-CBCT on confirmed acute ischemic or hemorrhagic stroke has not been done before. The sample size estimations aims to prove diagnostic quality non-inferiority compared to CT according to performance goals below.

The sample size for the primary endpoint is trait-based, using ten [10] ASPECTS regions for each subject. To evaluate the diagnostic accuracy of DE-CBCT compared to CT, it is estimated that a sample size of 137 is required to render a power of 90% (target accuracy of 0.90, performance goal lower boundary of 0.80, one-sided alpha of 0.025). For this endpoint, a minimum sample size of 14 subjects is required.

The first secondary endpoint (vessel tree visibility) is also trait-based, using eleven [11] arterial regions for each subject. To evaluate the proportion of regions rated equal or superior to CT, it is estimated that a sample size of 126 is required to render a power of 80% (target proportion of 0.90, performance goal lower boundary of 0.80, one-sided alpha of 0.0125, adjusted for multiple secondary endpoints). For this endpoint, a minimum sample size of 12 subjects is required.

IGT Systems	Clinical Research Protocol Next Generation X-ray Imaging System (NEXIS)	Doc ID: XCY612-130814 Rev: 01 Page 34 of 57
-------------	----------------------------------------------------------------------------	---------------------------------------------------

The second secondary endpoint is defined as diagnostic accuracy to determine the presence of intracranial hemorrhage, comparing DE-CBCT to CT (reference). The endpoint is subject-based and it is estimated that a sample size of 20 is required to render a power greater than 95% (target accuracy of 0.9999, performance goal lower boundary of 0.80, one-sided alpha of 0.0125, adjusted for multiple secondary endpoints). The sample size includes both subjects with hemorrhage and negative controls, preferably with 0.5 hemorrhage prevalence, with a threshold of at least a third of our subjects to have an intracranial hemorrhage. For this endpoint, a minimum sample size of 20 is required.

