In total, the minimum sample size required is 20 subjects, of which two-thirds have ischemia, one-third have intracranial hemorrhage, and at least half must have done a contrast enhanced DE-CBCT. Our estimated necessary sample size is 29 subjects, taking algorithm optimization and potential invalid data into account.

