8.7. Secondary objectives

8.7.1. Vessel tree visibility

Endpoint (1st Secondary endpoint)

Proportion of contrast-enhanced DE-CBCT rated non-inferior (i.e. equal or superior) vessel visibility compared to CTA (reference standard).

Applicable subjects

All subjects with a contrast enhanced DE-CBCT scan and diagnostic CT angiography.

Data

- Radiologist rating
 - Inferior/Equal/Superior
 - Distal ICA (dICA)
 - A1-A2
 - Lenticulostriate arteries

IGT Systems	Clinical Research Protocol Next Generation X-ray Imaging System (NEXIS)	Doc ID: XCY612-130814 Rev: 01 Page 36 of 57
-------------	----------------------------------------------------------------------------	---------------------------------------------------

- M1
- M2
- M3-M4
- Distal Vertebrales
- Basilar
- Basilar perforating branches
- AICA-PICA-SCA
- P1-P2

Analysis

Images are evaluated by radiologists using CT angiography as reference standard and the proportion of equal or superior vessel visibility rating in abovementioned vessel territories is defined.

Hypothesis:

$$\begin{aligned} H_0: \pi_2 &\leq 0.80 \\ H_1: \pi_2 &> 0.80 \end{aligned}$$

Where π_2 is the observed proportion of equal or superior vessel visibility and 0.80 is the performance goal.

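### The combined minimum of 20 subjects secures only 10 contrast-enhanced subjects for vessel visibility, against the 12 that section 8.2 requires

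*Combined protocol and SAP*

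**What the plan says.** Section 8.2 sizes each endpoint separately and then combines them.

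- **Primary (ASPECTS accuracy):** 137 regions at 10 per subject, 90% power; "For this endpoint, a minimum sample size of 14 subjects is required". Section 8.6.1 restricts it to subjects with ischemic stroke on CT.
- **First secondary (vessel visibility):** with 11 regions per subject, "it is estimated that a sample size of 126 is required to render a power of 80"%, and then "For this endpoint, a minimum sample size of 12 subjects is required". Section 8.7.1 defines who counts: "All subjects with a contrast enhanced DE-CBCT scan and diagnostic CT angiography".
- **Second secondary (hemorrhage detection):** 20 subjects, "preferably with 0.5 hemorrhage prevalence, with a threshold of at least a third of our subjects to have an intracranial hemorrhage".
- **Combined minimum:** "20 subjects, of which two-thirds have ischemia, one-third have intracranial hemorrhage, and at least half must have done a contrast enhanced DE-CBCT". The planned number is 29, to allow for algorithm optimization and invalid data.

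The Summary and section 6.6.1 repeat the combined minimum with its shares. Neither gives the count of 12.

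On subjects without contrast, section 5.5 states: "If the subject is deemed inappropriate to receive iodine contrast agent, only imaging without iodine contrast agent will be done". On replacement, section 6.6.2 begins: "Subjects in the study will be replaced in case of withdrawal of consent or if subject is found ineligible for the study". It adds movement during acquisition, and 6.6.1 adds withdrawal by the investigator.

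**The concern.** A combined minimum should guarantee every per-endpoint minimum it is built from. Here the contrast share, applied to 20, gives a lower number than the requirement set just before it. Staff working from the Summary or 6.6.1 see only the share. They could close enrolment with the stated minimum met while a secondary endpoint with a formal hypothesis test is below its planned power. The ischemia share raises the same question for the primary endpoint, on a smaller scale.

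**Working it through.** **Inputs (section 8.2).** Null proportion 0.80 and target 0.90 for both region-based endpoints. One-sided alpha is 0.025 (primary) and 0.0125 (vessel visibility). Regions per subject are 10 and 11.

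**Reproducing the plan.** Use a one-sample exact binomial test: take the smallest critical count r with P(X ≥ r | n, 0.80) ≤ alpha, with power P(X ≥ r | n, 0.90). The smallest n reaching the target power is:

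- Primary: n = 137, r = 119, alpha 0.0245, power 0.910; 137/10 = 13.7, so 14 subjects.
- Vessel visibility: n = 126, r = 111, alpha 0.0118, power 0.809; 126/11 = 11.45, so 12 subjects.
- Hemorrhage (target 0.9999, alpha 0.0125): n = 20, r = 20, alpha 0.0115, power 0.998.

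All three stated sizes are reproduced. The first two treat regions within a subject as independent.

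**Contrast share.** 20/2 = 10 subjects and 10 × 11 = 110 regions, which is 2 subjects and 16 regions short. Twelve of 20 is 60%. A one-half share first guarantees 12 at a total of 23 (23/2 = 11.5, rounded up).

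**Ischemia share.** 20 × 2/3 = 13.3. One-third of 20 is 6.7, so the hemorrhage threshold needs 7. With separate groups 20 − 7 = 13 are ischemic, one short of 14. Separate groups of 14 and 7 need 21 subjects.

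**Power at these counts.** The normal approximation is Φ{[0.10√n − z·√(0.8·0.2)] / √(0.9·0.1)}, with z = 2.241 for vessel visibility and 1.960 for the primary. For n = 110: (1.0488 − 0.8966)/0.3 = 0.507, giving 0.694.

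| Endpoint | Subjects | Regions | Critical count | Exact power | Normal approx. |
|---|---|---|---|---|---|
| Vessel visibility | 10 | 110 | 98 | 0.695 | 0.694 |
| Vessel visibility | 11 | 121 | 107 | 0.772 | 0.751 |
| Vessel visibility | 12 | 132 | 116 | 0.832 | 0.800 |
| Primary | 13 | 130 | 114 | 0.847 | 0.882 |
| Primary | 14 | 140 | 122 | 0.894 | 0.908 |

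Exact power moves in a sawtooth, so single values need care. For vessel visibility the two methods agree at 110 regions, and no n from 104 to 125 reaches 0.80 on the exact test (highest 0.782, at n = 120). For the primary, 130 regions is a sawtooth low point: at 131 exact power is 0.897. The primary loss is therefore about 3 points (normal) to 5 points (exact).

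**At the planned 29.** Half of 29 rounds up to 15 contrast subjects, 3 above 12. One-third rounds up to 10 hemorrhagic, leaving 19 ischemic, 5 above 14. At the preferred hemorrhage prevalence of 0.5 with separate groups, 14 or 15 are ischemic, a margin of 0 or 1.

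**The case against.** The strongest reply is that the statements do not conflict. The share is a floor, 12 of 20 satisfies both, and the requirement of 12 is not withdrawn. That is true, but a floor is what a minimum guarantees, and this one permits 12 without requiring it. The contrast scan is also not sufficient for the endpoint: section 6.5 lets transferred patients have only neCT and CTP, so a contrast DE-CBCT may lack its CTA comparator.

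Second, the plan is for 29, and at the stated shares 29 clears both counts. This stands as a limit on the point. It does not remove it, because the nine subjects above 20 are there for algorithm optimization and invalid data, and the plan does not say how many it expects to lose or from which group.

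Third, the ischemia gap depends on separate groups and on rounding the hemorrhage share up. The sentence describes findings rather than exclusive arms, and section 8.8.3 foresees hemorrhagic transformation of ischemic stroke, so overlap could close a one-subject gap. This is fair. The ischemia part is a matter of wording: the plan does not say whether a subject with both findings counts in both groups.

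Fourth, independence of regions is doubtful, so even 12 subjects may not give 80%. The documents give no within-subject correlation. With assumed values of 0.05 to 0.2 and a design effect of 1 + 10ρ, normal-approximation power for vessel visibility is about 45% to 17% at 10 subjects and 56% to 22% at 12. The figures in the table therefore show the gap on the plan's own basis and should not be read as the power that the trial will have.

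**Conclusion.** The concern holds. For vessel visibility, the combined minimum secures 10 subjects against the 12 required, and neither rounding nor overlap between groups closes that gap. Assuming independent regions, as the plan's figures do, power falls from the stated 80% to about 69%. For the primary endpoint the gap is one subject and about 3 to 5 points of power, and it exists only if the ischemic and hemorrhagic groups are separate. Both gaps are at the stated minimum of 20. At 29 they are absent unless more than 3 contrast or more than 5 ischemic subjects are lost at the stated shares; the ischemic margin shrinks to 0 or 1 at the preferred hemorrhage prevalence with separate groups. This should be corrected, but it does not call the design into question.

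**What to change.** In the Summary, 6.6.1 and 8.2, replace the shares with counts of evaluable subjects:

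- at least 12 who meet the applicability rule of 8.7.1 (contrast DE-CBCT and diagnostic CTA);
- at least 14 with ischemic stroke;
- at least one-third with hemorrhage, with either a total of 21 if the groups are separate or a statement that a subject with both findings counts in both.

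State how the count of 12 will be reached when enrolled subjects have no contrast scan, since the replacement rules do not cover them. This concerns enrolment counting only, not who may receive contrast. State the expected losses within the 29, by group.

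Alternatively, keep 20 and the shares, and restate the power at their floors: about 69% for vessel visibility and about 85–88% for the primary endpoint, with the explicit caveat that both assume independent regions within a subject.

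The cost is wording in three places. No extra enrolment is needed if losses from the 29 stay within 3 contrast and 5 ischemic subjects at the stated shares. If the 0.5 hemorrhage prevalence is pursued with separate groups, expected losses should be set out before 29 is called sufficient.

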8.3. Statistical methods

All variables will be summarized by descriptive statistics. The statistics for continuous variables includes mean, median, standard deviation, 95% confidence interval for the means, and the number of observations. For categorical variables, number of events, event rate, and 95% confidence interval for the event rate will be presented.

For categorical variables, the Fisher's Exact or chi-squared test will be used. For numerical variables, Student's t-test will be applied for image quality parameters such as signal-to-noise ratio (SNR) and contrast-to-noise ratio (CNR). For ordinal rank variables concerning radiologist interpretation, the Wilcoxon test will be used. The decision to use non-parametric or parametric tests will be based on the result from Shapiro-Wilk test as well as the distribution of the data on a P-P plot.

Receiver operating characteristic (ROC) curves will be constructed and accuracy as well as area under the curve (AUC) will be used to assess image diagnostic performance, where applicable. Sensitivity, specificity, negative and positive predictive value will be assessed with optimal cut off, where applicable. The DeLong test will be applied when comparing ROC curves. The Kappa coefficient will be used to evaluate interrater and within-observer agreement, where applicable. Additional statistical methods may be used in accordance with relevant literature (33). A biostatistician is involved in planning and executing the statistical analyses.

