8.8. Additional Objectives – 3D diagnostic imaging

8.8.1. Ischemic stroke diagnostic accuracy, vessel tree visibility and hemorrhage detection accuracy compared to regular CBCT

Applicable subjects, data and analysis same to that of primary and secondary endpoints, but using conventional CBCT image data (acquired from the top layer of the investigational device) as reference.

IGT Systems	Clinical Research Protocol Next Generation X-ray Imaging System (NEXIS)	Doc ID: XCY612-130814 Rev: 01 Page 37 of 57
-------------	----------------------------------------------------------------------------	---------------------------------------------------

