8.9. Additional Objectives – 3D image quality parameters

8.9.1. Objective image quality parameters

Applicable subjects

All subjects.

Data

HU (or equivalent), standard deviations, CNR and SNR

- Central vs peripheral location in the image
- Water

IGT Systems	Clinical Research Protocol Next Generation X-ray Imaging System (NEXIS)	Doc ID: XCY612-130814 Rev: 01 Page 39 of 57
-------------	----------------------------------------------------------------------------	---------------------------------------------------

- Fat
- Grey matter
- White matter
- Blood
- Iodine
- Calcium (bone)

Analysis

Absolute numerical variables, mean and standard deviations of image quality indexes will be compared to reference standards (CT, DECT, CBCT).

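### Section 8.3 assigns independent-groups tests to categorical outcomes that are compared within subject, and leaves the version of the t-test and Wilcoxon test open

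*Combined protocol and SAP*

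**What the plan says.** Section 8.3 is where tests are assigned to types of variable:

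- Categorical: Fisher's "Exact or chi-squared test will be used".
- Numerical: "Student's t-test will be applied for image quality parameters such as signal-to-noise ratio (SNR) and contrast-to-noise ratio (CNR").
- Ordinal: "For ordinal rank variables concerning radiologist interpretation, the Wilcoxon test will be used".

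A Shapiro-Wilk test and a P-P plot decide between parametric and non-parametric tests. The section does not mention pairing, the signed-rank test, McNemar's test or clustering.

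The comparisons are described elsewhere. The study has a single group (6.1), and each subject's own CT, including DECT, is the comparator (6.2.1). Section 8.8.1 repeats the primary and secondary analyses "using conventional CBCT image data (acquired from the top layer of the investigational device) as reference". In 8.9.1 the "mean and standard deviations of image quality indexes will be compared to reference standards (CT, DECT, CBCT"). Three neuroradiologists read the images (8.1).

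Sections 8.6 and 8.7 state three one-sample hypotheses against 0.80 without naming a test. Section 8.2 sizes them at 137 regions, 126 regions and 20 subjects.

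**The concern.** Fisher's exact test and the chi-squared test, applied to a modality-by-result table, treat the two rows as different people. Here the same person is in both rows. Subjects who are easy or hard to image tend to be so on every modality, and CBCT even shares its acquisition with DE-CBCT, so positive correlation is the natural expectation. A test that ignores it uses too large a variance: its type I error falls below 5%, and a real difference is harder to detect.

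For SNR, CNR and HU the issue is different. Student's t-test has a paired and a two-sample form, and Wilcoxon has a signed-rank and a rank-sum form. The plan does not choose, and the choice can change the result materially.

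**Working it through.** **1. Confirmatory hypotheses.** Inputs from 8.2, one-sample exact binomial against 0.80: reject when successes reach k, with alpha = P(X ≥ k | 0.80) and power = P(X ≥ k | target).

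| Endpoint | n | Target | k | Alpha (limit) | Power (stated) |
|---|---|---|---|---|---|
| Primary | 137 | 0.90 | 119 | 0.0245 (0.025) | 91.0% (90%) |
| First secondary | 126 | 0.90 | 111 | 0.0118 (0.0125) | 80.9% (80%) |
| Second secondary | 20 | 0.9999 | 20 | 0.0115 (0.0125) | 99.8% (>95%) |

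All three reproduce. The intended tests are one-sample, and the tests named in 8.3 do not enter them.

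**2. Why ignoring pairing matters.** For n pairs with common SD σ and within-subject correlation ρ, the mean difference has variance 2σ²(1−ρ)/n. A two-sample test uses 2σ²/n. At ρ = 0.7 the true variance is 30% of the one used. At ρ = 0 nothing is lost.

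**3. SNR/CNR.** n = 20 (minimum) and 29 (planned) come from 8.2. The difference of 0.5σ and the values of ρ are assumptions. Tests are two-sided at 0.05. Paired power comes from the noncentral t with n−1 degrees of freedom and noncentrality 0.5√n/√(2(1−ρ)); at n = 20 this is 1.58, 2.24, 2.89 and 5.00. Two-sample figures are simulated.

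| ρ | Two-sample size, n=20 | Two-sample power, n=20 | Paired power, n=20 | Two-sample power, n=29 | Paired power, n=29 |
|---|---|---|---|---|---|
| 0 | 5.0% | 34% | 32% | 46% | 45% |
| 0.5 | 0.8% | 29% | 56% | 45% | 74% |
| 0.7 | 0.1% | 25% | 78% | 44% | 92% |
| 0.9 | 0.0% | 17% | >99% | 42% | >99% |

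**4. Binary outcome, one reading per subject and modality.** Assumed proportions are 0.80 vs 0.80 for size and 0.90 vs 0.70 for power, with assumed correlation φ. The both-positive cell is p₁p₂ + φ√(p₁q₁p₂q₂). For example, 0.63 + 0.5×√(0.09×0.21) = 0.699, leaving discordant cells of 0.201 and 0.001. Multinomial probabilities were summed over all possible tables; chi-squared is uncorrected. Entries are size / power in percent.

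| n, φ | Fisher | Chi-squared | Exact McNemar | Mid-p McNemar |
|---|---|---|---|---|
| 20, 0 | 2.3 / 24 | 5.0 / 36 | 1.5 / 19 | 3.4 / 29 |
| 20, 0.3 | 0.7 / 20 | 2.1 / 33 | 0.7 / 20 | 2.1 / 34 |
| 20, 0.5 | 0.2 / 16 | 0.8 / 29 | 0.2 / 20 | 1.0 / 37 |
| 29, 0 | 2.1 / 35 | 4.8 / 48 | 2.1 / 34 | 4.1 / 44 |
| 29, 0.3 | 0.6 / 32 | 2.0 / 48 | 1.5 / 44 | 3.4 / 57 |
| 29, 0.5 | 0.2 / 29 | 0.7 / 47 | 0.7 / 53 | 2.2 / 71 |

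The named tests become more conservative as φ rises. The gain from McNemar depends on its version. At 20 subjects the exact form does not beat chi-squared, while mid-p does once φ reaches about 0.3, though only by one point there.

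**The case against.** Most of the case against a stronger claim stands.

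- A reader might infer that 8.3 names wrong tests throughout. It does not. Student's t-test and the Wilcoxon test include paired forms, so for SNR, CNR and HU the gap is an unspecified version.
- A reader might infer that the primary and secondary results are at risk. Step 1 shows that they are not.
- A reader might infer that true differences in accuracy between DE-CBCT and CBCT or CT would be missed. The documents do not support this. CT is the reference, so it has no accuracy of its own to compare. Section 8.8.1 makes CBCT the reference under the same analysis, which again reads as one proportion against 0.80. A test of two accuracies is not clearly planned.
- Many ratings are inferior/equal/superior or more/equal/less, so the pairing is already inside the rating. Section 8.8.5 plans only to report proportions. The outcomes exposed to a two-sample categorical test are few.
- The power loss rests on correlations that the documents do not give, the error is conservative, and the additional objectives carry no stated power.
- Section 8.3 adds: "Additional statistical methods may be used in accordance with relevant literature (33"). It also involves a biostatistician, and section 8 requires departures to be documented.

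The last item does not close the gap. The clause names no method, and it leaves the choice between tests with different p-values until after the data are seen. For categorical variables the only rule given is an independent-groups one, and it would govern any test run in 8.8.5 or 8.9.2.

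**Conclusion.** The concern holds in limited form. For binary outcomes recorded per modality, the named categorical tests assume independence that the design lacks, and their p-values are too large under positive correlation: at 20 subjects and φ = 0.5, Fisher's actual size is 0.2% and chi-squared's 0.8%, against a nominal 5%. For the t-test and Wilcoxon test the defect is an unstated version. The cost if the two-sample t-test were run goes from none at correlation 0 to 25% against 78% power at 0.7, for 20 subjects and 0.5 SD.

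These sizes rest on assumed correlations, effects and proportions. Pairs with DECT would number fewer than the full sample, because DECT is done only in group 3.II and in thrombolysed subjects of group 3.I (6.5, Table 3). The consequence is confined to the additional objectives. Whether regions within a subject are independent, as the sizing in 8.2 implies, is a separate question that this point does not settle.

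**What to change.** In 8.3:

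1. For within-subject modality comparisons of binary outcomes, replace Fisher's exact and chi-squared with mid-p McNemar, using a subject-clustered version where several regions or readers contribute.
2. State the paired t-test or the Wilcoxon signed-rank test for SNR, CNR and HU.
3. Name the one-sample test against 0.80 at the alphas in 8.2: exact binomial for hemorrhage, subject-clustered for the two region-based endpoints. The 95% interval promised in 8.3 matches the primary one-sided 0.025 but not the 0.0125 of the secondary endpoints, so it cannot stand in for all three.

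This is a change of wording with no added subjects or scans, best made before images are read. There is a small downside: at about 20 subjects with little correlation, mid-p McNemar has less power than uncorrected chi-squared (29% vs 36% at φ = 0 in step 4), and the exact form clearly less (19%). That is why mid-p is preferred here.

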3.4. Evaluation of clinical testing

As no commercially available flat panel detector system has energy separation capabilities today, the investigation NEXIS devices has not been tested clinically. This study will collect the first clinical data. Before enrollment of subjects, the study will be registered in the ClinicalTrials.gov database.

4. Risks and benefits of the investigational device and clinical research

The NEXIS system is not CE marked and is referred to as an investigational device that needs approval from both the Swedish Medical Products Agency (MPA, Läkemedelsverket) and the Ethics committee (Etikprövningsmyndigheten) before it can be used in this clinical trial.

Clinical benefits

No direct benefit will be added for the patients. However, their participation in this study will provide valuable scientific information and guidance towards an improved diagnostic and treatment approach for future patients with the same diagnosis. Our strategy of diagnosing and treating stroke in the same room has the potential to lower the time elapsed before treatment and thus give patients a better chance of successful reperfusion of brain tissue (25).

Risk assessment

The risk assessment process that Philips follows is in accordance with ISO 14971. This will ensure that the level of risk is acceptable prior to the start of the study. A detailed overview of the risk assessment can be found in the Investigator Brochure section 5 [REF-1].

The Overall Conclusion of the risks vs benefits analysis is that:

- Both device related risks and the study related risks have been considered and mitigation controls in place are effective
 - All device related risks have been reduced as far as possible and individual residual risks after mitigation are classified as acceptable.
 - Risks to the subject associated with the clinical procedure required by the study plan are limited to additional X-ray dose and iodine contrast and can be justified.
- The overall residual risk is acceptable;
- Based on the overall safety profile, AlluraNEXIS Investigational Device can be safely used in clinical practice.

5. Objectives

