8.1. Image data management

The raw image data with added dual energy properties (DE-CBCT) will be processed using novel reconstruction and segmentation techniques. During the intervention only the product reconstruction algorithm is available for raw image data acquired by the first layer of the detector and images reconstructed in this fashion will be identical to current CBCT.

After the intervention the DE-CBCT raw image data will be reconstructed with the novel spectral reconstruction software and then evaluated by three independent neuroradiologists (not involved in the clinical investigation) for subjective outcome variables. The first cases will also be used to iterate and optimize reconstruction algorithms. Images will be processed on-site and off-site. For ordinal outcome variables comparing the subjective performance of DE-CBCT and CBCT to CT, CTA and CTP (such as the first secondary objective), neuroradiologists will have access to both DE-CBCT and reference image data concurrently. For the primary and second secondary objective DE-CBCT and reference image, data will be cleaned from any information regarding acquisition technique and evaluated randomly and separated in time, in order to limit the possibility of bias.

A secure image data repository will be set up at Karolinska University Hospital, the access to which will be provided through IntelliSpace Discovery (ISD) that will serve as the interfacing client for managing and logging the access of data by authorized personnel involved in this study. No additional software will be required by the user to access the data as the ISD client runs in chrome web browser with a zero footprint i.e., no data will be stored on user's computer while using the ISD interface.

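### Section 8.3 plans an optimal cut-off without giving its source or any correction; for scored or continuous additional measures in 20–29 subjects this would overstate sensitivity and specificity

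*Combined protocol and SAP*

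**What the plan says.** Section 8.3 plans ROC curves and says that "accuracy as well as area under the curve (AUC) will be used to assess image diagnostic performance, where applicable". The next sentence reads: "Sensitivity, specificity, negative and positive predictive value will be assessed with optimal cut off, where applicable". Neither sentence names the measures concerned, the optimality criterion, the data from which the cut-off is taken, or any cross-validation, bootstrap correction or validation set.

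On sample size, section 8.2 says "In total, the minimum sample size required is 20 subjects" and "Our estimated necessary sample size is 29 subjects, taking algorithm optimization and potential invalid data into account". For hemorrhage it asks for a sample "preferably with 0.5 hemorrhage prevalence, with a threshold of at least a third of our subjects to have an intracranial hemorrhage".

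On other sources of a cut-off, section 3.4 says of the device: "This study will collect the first clinical data". Section 8.1 adds that "The first cases will also be used to iterate and optimize reconstruction algorithms", and sets no cases aside for choosing or checking a cut-off.

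**The concern.** A cut-off picked because it separates this sample best also fits the sample's noise. Sensitivity and specificity read off the same subjects at that cut-off are then higher, on average, than the same cut-off would give in new patients. The bias grows as the sample shrinks, and 20–29 subjects is small. Many of the additional measures apply only to subjects with ischemia, hemorrhage or thrombus (8.8.2 to 8.8.4), so the number available would be smaller still.

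The study is described as a proof of concept whose results would prompt further work (2.12, 5.5), and section 15 foresees about two publications. Uncorrected figures could enter either without a caveat. Nothing confirmatory is at stake.

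**Working it through.** **1. What the tested endpoints use.** The documents give no figure for the cut-off itself. Their stated sample sizes show how the three hypotheses are tested, and all three reproduce as one-sample exact binomial tests against a fixed 0.80:

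- Primary (8.6.1): n = 137 regions, reject at 119 or more, one-sided alpha 0.0245, power 0.910 at 0.90. 137/10 = 13.7, so 14 subjects.
- First secondary (8.7.1): n = 126 regions, reject at 111 or more, alpha 0.0118, power 0.809 at 0.90. 126/11 = 11.5, so 12 subjects.
- Second secondary (8.7.2): n = 20 subjects, reject only at 20 of 20, alpha 0.0115, power 0.998 at 0.9999.

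The data are regional ASPECTS agreement, a three-level rating whose success categories are fixed in advance, and a yes/no read. None needs an optimised cut-off, so the inflation from this source is zero for all three.

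**2. Inputs for a measure that does need a cut-off.** From section 8.2: n = 20 or 29, prevalence one third or one half. The prevalence is specified for hemorrhage and is borrowed here as a plausible range. Assumed, because the documents give no value: true AUC from 0.75 to 0.95, equal-variance binormal scores, and the Youden criterion (maximise sensitivity + specificity).

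**3. Model.** Negatives are N(0, 1) and positives N(d, 1), with d = √2 × Φ⁻¹(AUC). The best achievable cut-off gives sensitivity = specificity = Φ(d/2). For AUC 0.90: d = 1.414 × 1.282 = 1.812, and Φ(0.906) = 0.818.

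**4. Simulation.** In each simulated data set the cut-off is chosen on the sample. Excess = (apparent sensitivity + specificity) − (the same cut-off's sensitivity + specificity in new patients), averaged over 20,000 data sets per setting.

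Worked case, n = 20 with 7 positives, AUC 0.90, continuous measure:
- Apparent: 0.885 + 0.876 = 1.761.
- New patients: 0.733 + 0.843 = 1.576.
- Excess: 1.761 − 1.576 = 0.185 (0.186 before rounding).
- The best achievable sum is 0.818 + 0.818 = 1.636, so the apparent figure exceeds even that by about 0.125.

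Excess in sensitivity + specificity (continuous / five-level score):

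| Setting | AUC 0.80 | AUC 0.90 | AUC 0.95 |
|---|---|---|---|
| n = 20, prevalence 1/3 | 0.212 / 0.131 | 0.186 / 0.113 | 0.164 / 0.101 |
| n = 20, prevalence 1/2 | 0.190 / 0.122 | 0.161 / 0.103 | 0.141 / 0.089 |
| n = 29, prevalence 1/3 | 0.175 / 0.104 | 0.151 / 0.086 | 0.132 / 0.076 |
| n = 29, prevalence 1/2 | 0.160 / 0.097 | 0.131 / 0.078 | 0.114 / 0.069 |

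At AUC 0.75, continuous, sensitivity + specificity − 1 appears as 0.52–0.54 at n = 20 and 0.50–0.51 at n = 29, while the chosen cut-off delivers 0.32–0.33. The largest gap is 0.54 − 0.32 = 0.22. The five-level score reaches about 0.14.

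**5. How the excess divides.** At prevalence one third it falls mainly on sensitivity. For AUC 0.75–0.85 it is about 11–14 points on sensitivity and 5–8 on specificity when the cut-off lies midway between observed values. The worked case places the cut-off at an observed value, which shifts more onto sensitivity: 0.885 − 0.733 = 0.152, against 0.876 − 0.843 = 0.033. The sum depends little on this choice.

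**6. Region-level measures.** With 14 × 10 = 140 independent regions, one third positive, the excess over AUC 0.70–0.95 is only 0.02–0.08. Clustering of regions within subjects would raise it.

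**The case against.** The strongest reply is that the sentence is generic. It carries the qualifier "where applicable" in substance, and no measure in sections 8.6 to 8.9 is assigned an ROC cut-off. HU, SNR and CNR are to be compared as means and standard deviations. Hemorrhage and thrombus are characterised against CT or DECT without a dichotomised target. Tissue separation is rated in categories, and perfusion characterisation is labelled exploratory. AUC, which involves no cut-off, is already a planned summary. All of this stands: one cannot point to a named analysis that is certain to be biased, and the settings simulated are illustrative.

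A reader might infer three stronger things, none of which the documents support:

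- That the plan says the cut-off will be found on the same subjects. It does not give a source. The inference rests on the position of the sentence after the ROC plan, the lack of earlier clinical data, and the absence of a second cohort.
- That every sensitivity and specificity in the study, including the primary and hemorrhage results, would be inflated. Step 1 shows that the tested endpoints need no such cut-off, and the hemorrhage read is already yes/no.
- That sensitivity and specificity would each be inflated by the same amount. Halving the summed excess hides an uneven split when positives are the minority.

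What the reply does not remove is that 8.3 states a rule for four reported statistics and leaves open the one detail that decides whether they are biased.

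**Conclusion.** The point holds as a low-cost improvement to the exploratory analyses. If 8.3 is followed in its natural reading, sensitivity + specificity for a subject-level additional measure would be overstated by about 0.11–0.22 (continuous) or about 0.07–0.14 (five-level score) at 20–29 subjects, and by less for region-level measures. The size rests on the assumed AUCs of 0.75–0.95, the binormal model, the Youden criterion and prevalence of one third to one half; the upward direction does not depend on the AUC chosen. PPV and NPV come from the same two-by-two table, but their bias was not computed and no size is claimed. The three hypothesis tests are unaffected. If the sponsor means an externally fixed cut-off, one sentence saying so would settle the matter.

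**What to change.** In section 8.3, list any measure that needs a cut-off. For each, fix the cut-off before the reads are unmasked. Where that is not possible, state the criterion, make AUC the main summary, and report sensitivity, specificity, NPV and PPV with bootstrap optimism correction or leave-one-subject-out estimation. Repeat the cut-off search inside every resample, resample by subject so that regions from one patient stay together, and label the results exploratory.

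No extra subjects, scans or reads are needed. The cost is a few lines of SAP text, a little more analysis code, and slightly less favourable figures.
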